## **6.3 Other Exploratory Endpoints**

### **6.3.1 Pharmacokinetics**

Sparse PK sampling for determination of GS-248 levels in plasma will be performed on all subjects at Visit 2, Visit 3 and Visit 4.

One PK blood sample will be drawn at Visit 2 shortly after the ECG assessment is conducted post IMP administration and one PK blood sample will be drawn at Visit 3 any time during the visit.

At Visit 4 the IMP dose is administered at the study site. Two PK blood samples will be drawn from subjects in the sparse PK group. One sample is drawn immediately before IMP administration and the second sample is drawn either at 120 minutes after IMP administration or, if the subject is enrolled to cold challenge assessments, at 175 minutes after IMP administration.

In approximately 30 subjects, rich PK sampling will be performed at Visit 4, with an additional 6-7 PK samples to be drawn (see [APPENDIX 4](#)). Time points for all rich PK sampling at Visit 4 will be pre-dose, 30-, 60-, 90-, 120-, 175-, 240- and 360-min post dose. If feasible, one additional sample should also be drawn at 480 min or as late as possible post dose.

Exact times of IMP administration and time for sampling will be captured in the eDiary and eCRF.

Blood samples will be centrifuged, and separated plasma will be shipped to a bioanalytical laboratory.

The combined data from sparse and rich PK sampling will be incorporated into model-based population PK analyses, the results of which are to be reported separately.

### 6.3.2 Pharmacodynamics

- PGE2 levels in whole blood: In up to 30 subjects blood samples will be drawn at Visit 2 and Visit 4 pre-IMP administration to assess change in PGE2 level in whole blood *ex vivo* from baseline to week 4.
- Levels of PGEM, PGIM and TXM in urine: Spot morning urine samples will be collected by subjects at home and brought to the study site at Visit 2 and Visit 4 for assessment to determine change in levels of PGEM, PGIM, and TXM in urine from baseline to week 4.
- Biomarkers for inflammation and endothelium dysfunction: Blood samples will be collected from all subjects at Visit 2 and Visit 4 pre-IMP administration for analysis of hsCRP, Endothelin-1, sE-selectin, ICAM1, TNF, IL-1b, IL-4, IL-6, IL-10, s-PECAM1 CXCL-4, CD40L and von Willebrand factor to determine change in levels of biomarkers in blood/plasma from baseline to week 4.
- Expression of platelet surface markers: In up to 20 subjects blood samples will be drawn at Visit 2 and Visit 4 pre-IMP administration for analysis of surface markers of platelet activation by FACS analysis to determine change from baseline to week 4.
- Microvascular volume in skin/nailfold: At one pre-defined site, microvascular volume in skin/nailfold (see [APPENDIX 6](#) and [APPENDIX 7](#)) will be performed on consenting subjects twice at Visit 2 and Visit 4 (pre-IMP administration and at expected Cmax by D-OCT), and once at Visit 3 and Visit 5, to determine change in microvascular volume from baseline to week 4.
- Collection of blood and urine samples for Biobank storage: One urine sample each from Visit 2 and Visit 4 and four plasma samples, two from Visit 2 and Visit 4 will be stored in a Biobank for up to 3 years after study end for potential future analysis of inflammatory biomarkers and biomarkers for endothelial dysfunction.

## 7 STUDY CONDUCT

### 7.1 Observations by Visit

Visits should occur as specified in the Overall Schedule of Assessments (see [APPENDIX 2](#)). All times should be recorded using the 24-hour clock (e.g., 23:20, not 11:20 pm).

#### 7.1.1 Screening (Visit 1)

The following procedures and assessments are to be completed at the Screening Visit (Day -21 to -14) at time points designated in the Overall Schedule of Assessments (see [APPENDIX 2](#)).

- Confirm ICF signature was obtained before any study related assessments are conducted.
- Record demographic data including sex, age and race
- Record medical/surgical history (including any risk factors)
- Record previous and current medications as well as history of vaccinations
- Complete full physical examination (including weight and height)
- Perform nailfold capillaroscopy (see [APPENDIX 7](#))
- Measure and record vital signs (heart rate and blood pressure)
- Perform 12-lead ECG
- Draw blood for clinical chemistry, haematology and thyroid hormone tests (see [Table 6.1](#))
- Urinalysis dipstick test (see [Table 6.1](#))
- SSc-related autoantibody status test, including antinuclear antibodies (ANA), Sci-70 antibody (anti-topoisomerase I), and anti-centromere antibodies (ACA) (this test does not need to be repeated for subjects who are re-screened)
- Urine pregnancy test in WOCBP, FSH assessment for women not of childbearing potential
- Verify eligibility (inclusion/exclusion criteria)
- Blood draw for hepatitis B, C, and HIV test
- Drug screen (for presence of alcohol or prohibited substances, e.g. cocaine)
- Issue of and training on use of the eDiary
- Perform and record the following assessments:
  - AEs

#### 7.1.2 Baseline Visit (Visit 2)

The following procedures and assessments are to be completed during the Baseline Visit (Visit 2, Day 1) at time points designated in the Overall Schedule of Assessments (see [APPENDIX 2](#)) and refer to Schedule of Assessments by Time – Visit 2 (see [Appendix 3](#)).

- Record current concomitant medications
- Perform abbreviated physical examination (statement regarding DUs)
- Measure and record vital signs (heart rate and blood pressure)

- Perform 12-lead ECGs pre- and post-IMP administration
- Draw blood for clinical chemistry and haematology tests (see [Table 6.1](#))
- Urinalysis dipstick test (see [Table 6.1](#))
- Urine pregnancy test in WOCBP,
- Verify eligibility (inclusion/exclusion criteria)
- Drug screen (for presence of alcohol or prohibited substances, e.g. cocaine)
- Review of eDiary to check for compliance (eligibility criterion) prior to study enrolment and randomization
- Collect blood and urine samples for storage at the Biobank
- Perform and record the following assessments:
  - Randomisation
  - ASRAP questionnaire (see [APPENDIX 11](#))
  - AEs
  - Initial IMP administration, to be taken with food
  - IMP distribution (a single bottle with sufficient doses until next visit)
  - Urinalysis: AA metabolites and U-creatinine (on the morning sample brought from home by subject)
  - PK sampling (sparse)
  - Blood biomarker sampling
- In addition, but only for subjects at pre-selected sites:
  - For subjects evaluated for enrolment to cold challenge: Measure finger temperature
  - Cold challenge and thermography (see [APPENDIX 5](#))
  - PGE2 levels in whole blood
  - Platelet activation (FACS)
  - Microvascular volume (see [APPENDIX 6](#))

### **7.1.3 Visit 3**

The following procedures and assessments are to be completed during Visit 3 (Day 15±2 days) at time points designated in the Overall Schedule of Assessments (see [APPENDIX 2](#)).

- Record current concomitant medications
- Perform abbreviated physical examination (statement regarding DUs)
- Measure and record vital signs (heart rate and blood pressure)
- Perform 12-lead ECG
- Draw blood for clinical chemistry and haematology tests (see [Table 6.1](#))
- Urinalysis dipstick test (see [Table 6.1](#))
- Review of eDiary
- Perform and record the following assessments:
  - ASRAP questionnaire (see [APPENDIX 11](#))
  - AEs

- IMP collection and compliance
- IMP distribution (a single bottle with sufficient doses until next visit)
- PK sampling (sparse)
- In addition, but only for subjects at pre-selected sites
  - Microvascular volume (see [APPENDIX 6](#))

#### **7.1.4 End of Treatment, Week 4 (Visit 4)**

The following procedures and assessments are to be completed during the Treatment Visit, Visit 4 (Day 28-2/+1 days) at time points designated in the Overall Schedule of Assessments (see [APPENDIX 2](#)) and refer to Schedule of Assessments by Time – Visit 4 (see [APPENDIX 4](#)).

- Record current concomitant medications
- Perform abbreviated physical examination (statement regarding DUs)
- Measure and record vital signs (heart rate and blood pressure)
- Draw blood for clinical chemistry and haematology tests (see [Table 6.1](#))
- Urinalysis dipstick test (see [Table 6.1](#))
- Urine pregnancy test in WOCBP,
- Drug screen (for presence of alcohol or prohibited substances, e.g. cocaine)
- Review of eDiary
- Collect blood and urine samples for storage at the Biobank
- Perform and record the following assessments:
  - ASRAP questionnaire (see [APPENDIX 11](#))
  - Global Impression of Change (Patient and Physician)
  - AEs
  - IMP administration at study site, to be taken with food
  - IMP collection and compliance
  - Urinalysis: AA metabolites and U-creatinine (on the morning sample brought from home by subject)
  - Blood biomarker sampling
  - PK sampling (sparse)
- In addition, but only for subjects at preselected sites:
  - Cold challenge and thermography (see [APPENDIX 5](#))
  - PGE2 levels in whole blood
  - Platelet activation (FACS)
  - Microvascular volume (see [APPENDIX 6](#))
  - PK sampling (rich)

#### **7.1.5 Follow-up (and/or Early Termination) Visit (Visit 5)**

The following procedures are to be completed during the Follow-up Visit (Day 42 to 49) at time points designated on the Overall Schedule of Assessments (see [APPENDIX 2](#)). In addition, any subject who withdraws or is withdrawn early from the study during

the Treatment Period, must complete this Follow-up Visit 2-3 weeks after their last dose of IMP.

- Record current concomitant medications
- Perform full physical examination (including weight)
- Measure and record vital signs (heart rate and blood pressure)
- Perform 12-lead ECG
- Draw blood for clinical chemistry and haematology tests (see [Table 6.1](#))
- Urinalysis dipstick test (see [Table 6.1](#))
- WOCBP given home pregnancy test to be used 35-40 days after their last dose of IMP (Visit 4).
- Review and collection of eDiary
- Perform and record the following assessments:
  - ASRAP questionnaire (see [APPENDIX 11](#))
  - AEs
- In addition, but only for subjects at preselected sites:
  - Microvascular volume (see [APPENDIX 6](#))

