- Subjects with a mean QTcF interval exceeding 450 msec are not eligible for randomization and will be excluded. Enrolled subjects with a mean QTcF exceeding 480 msec after the first dose will be withdrawn from further treatment as well as subjects with a mean QTcF interval exceeding 500 msec after 2 weeks treatment. This will minimize the potential for arrhythmia which is considered to be increased at QTcF intervals >500 msec.

- Subjects are not allowed to use moderate or strong CYP3A4 inhibitors within 5 terminal half-lives or one week, whichever is longer, prior to Visit 2 and throughout the treatment period i.e. day after Visit 4.
- IMP compliance will be recorded by subjects in an eDiary and this information will be collected on a daily basis. In addition, a scheduled visit is planned 2 weeks after the first dose of IMP: AEs will be recorded, and safety assessments performed at this visit.
- Subjects will have access to the clinic, either in person, or by telephone or email, at all times throughout the duration of the study.

Besides any potential risks related to the IMP, there may also be risks related to the medical devices used in the study. However, these are devices used in routine medical care and while they may cause transient discomfort, the associated risk is considered low and ethically justifiable.

Overall, the combined safety data from the pre-clinical studies and the studies in healthy volunteers have not revealed any safety concerns that would outweigh the expected benefits of the study. It is therefore concluded that the potential benefits from the study will outweigh the potential risks for the treated subjects.

More detailed information about the known and expected benefits and risks and reasonably expected adverse drug reactions (ADRs) of GS-248 is found in the current version of the Investigator's Brochure (IB).

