#### **4.5 Subject Withdrawal and Replacement**

As a result of treatment discontinuation, all subjects must complete an Early Termination visit (Visit 5) within 2-3 weeks after their last IMP dose.

There will be no replacement of withdrawn subjects.

The study participation of an individual subject must be discontinued, and no additional IMP doses given if the mean QTcF interval is above 480 msec post IMP administration at Visit 2, or above 500 msec at Visit 3.

The study participation of an individual subject may be discontinued prematurely for reasons such as:

- Adverse Event: Clinical or laboratory events that in the judgment of the investigator or the Sponsor and in the best interest of the subject constitute grounds for discontinuation. This includes serious and non-serious AE regardless of relation to IMP.
- Withdrawal of written informed consent: If a subject withdraws consent for disclosure of future information at the discontinuation of the study or after completion of the study, no further evaluations should be performed, and no additional data should be collected. The Sponsor may retain and continue to use data collected before the subject withdrew his/her consent. The reason for withdrawal of consent is only applicable if the subject denies any further contact with the site and no further data collection.

- Required treatment with any prohibited medication known or suspected to interfere with the pharmacological effect of IMP (see [Section 5.7](#)) as assessed by the Medical Monitor.
- Lack of study compliance: The subject's findings, or conduct, fails to meet protocol entry criteria or fails to adhere to the protocol requirements.
- Treatment unblinding.
- Any other condition which in the opinion of the Investigator no longer permits safe participation in the study.

A subject may discontinue participation in the clinical study at his/her own request at any time without stating a reason.

The Investigator can stop a subject's participation in the study at any time if continuation could lead to disadvantages for the subject which cannot be justified by the Investigator.

The reason for withdrawal of the subject must be documented by the Investigator together with all data collected until the day of premature study discontinuation including laboratory results and assessment of AEs.

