- Urine dipstick pregnancy test in WOCBP. At Visit 1, FSH assessment will be performed for women not of childbearing potential.
- For presence of alcohol or prohibited substances, e.g. cocaine
- Subjects will be given access to an eDiary and given instructions on how to use it at study enrolment. The eDiary will include the RCS, NRS pain scale, record of attacks (start time and finish time and date), IMP administration timepoints and reminders to subject.
- eDiaries will be completed for the final time and then “closed” so that no further data are entered.
- IMP administered together with food at the study site.
- Subjects bring a urine sample (first urination of the day) from home to the study site in the container provided.
- Predefined biomarkers (including hsCRP, Endothelin-1, sE-selectin, xICAM1, TNF, IL-1b, IL-4, IL-6, IL-10, s-PECAM1 CXCL-4, CD40L and von Willebrand factor).
- Two cold challenges will be performed, one pre- and another 180 mins post-IMP administration, see Appendix 2.1.
- Analysis of surface markers of platelet activation performed at a local laboratory.
- Two D-OCT assessments will be performed, one pre- and another 175 mins post-IMP administration
- WOCBP will receive a home pregnancy test to be used 35-40 days after their last dose of IMP.

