**APPENDIX 8: METHODS OF ASSESSMENT FOR EFFICACY ENDPOINTS**

Assessment	Description	Evaluation	Visit	Method of Collection
RP attack (eDiary)	A PRO Number and duration of attacks (for each attack: date, start time, stop time). Pain NRS for each attack.	-Mean number of RP attack during 7 days prior to Visit 4 compared with the mean number of RP attacks 7 days prior to Visit 2. -Cumulative duration of RP attacks during 7 days prior to Visit 4 minus the cumulative duration of RP attack during 7 days prior to Visit 4. - Mean change in NRS during 7 days prior to Visit 4 minus the mean NRS during 7 days prior to Visit 2	Daily from Visit 1 through to Visit 5	eDiary
Raynaud's Condition Score (RCS)	A PRO RCS is a validated numeric rating scale 0-10 (0 = No difficulty; 10 = Extreme difficulty) answering the question "What difficulty did you have today with your Raynaud's condition". To measure disease activity and Functional status	Mean score during 7 days prior to Visit 4 compared with mean score during 7 days prior to Visit 2.	Daily from Visit 1 through to Visit 5	eDiary
Physician Global Impression of Change	The clinician is answering the question "Considering all the ways in which Raynaud's symptoms affect your patient, compared to the start of treatment, how do you rate your patient's Raynaud's?" using a scale of; 1 = much better, 2 = a little better, 3 = no change, 4 = a little worse, 5= much worse.	The score at Visit 4 to be used	Visit 4	eCRF
Patient Global Impression of Change	A PRO The subject is answering the question "Considering all the ways in which Raynaud's symptoms affect you, compared to the start of treatment, how do you	The score at Visit 4 to be used	Visit 4	eDiary

Assessment	Description	Evaluation	Visit	Method of Collection
	rate your Raynaud's currently?" using a scale of; 1 = much better, 2 = a little better, 3 = no change, 4 = a little worse, 5 = much worse.			
ASRAP Questionnaire	A PRO	A newly developed outcome measure to assess the impact of RP physically and mentally, and how it impacts on subjects' daily life.	Visit 2 Visit 3 Visit 4 Visit 5	Paper

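### The eDiary closes at the Early Termination visit, so a subject who stops dosing in about the first week cannot supply a full week-4 diary; keeping it open to Day 28 is a cheap improvement

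*Protocol*

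**What the plan says.** **When early stoppers are seen.** Protocol 4.5 states that after treatment discontinuation "all subjects must complete an Early Termination visit (Visit 5) within 2-3 weeks after their last IMP dose". Section 7.1.5 gives the same timing for subjects who withdraw or are withdrawn: they "must complete this Follow-up Visit 2-3 weeks after their last dose of IMP". The schedule in Appendix 2 has a single Visit 5 column, which serves as both follow-up and early termination.

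**What happens to the diary there.** Section 7.1.5 lists "Review and collection of eDiary". The Appendix 2 footnote says that "eDiaries will be completed for the final time and then" closed, "so that no further data are entered". Appendix 8 gives the collection period as "Daily from Visit 1 through to Visit 5". No section keeps a diary open beyond the Early Termination visit.

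**What the primary endpoint needs.** Protocol 6.1.1 and SAP 5.1.1 use the seven days before Visit 4, which falls on Day 28 with a window of -2/+1 days. The FAS is everyone randomised and dosed. SAP 2.2 records that the earlier requirement for evaluable Visit 4 data was dropped.

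**The QTcF stop.** Section 4.5 reads: "The study participation of an individual subject must be discontinued, and no additional IMP doses given if the mean QTcF interval is above 480 msec" after dosing at Visit 2. Section 1.3 says that such subjects "will be withdrawn from further treatment".

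**The concern.** The primary outcome is reported from home. Protocol 7.1.6 itself relies on this when it argues that missed site visits should not affect the primary endpoint. Yet for early stoppers the diary's closing date is tied to a site visit that can fall before or inside the week-4 window. The protocol collects two to three weeks of off-treatment diary from these subjects and may then stop just short of the week that counts.

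These subjects stay in the primary analysis, so a value has to be supplied for them in one of two ways. If the diary is treated as missing, SAP 5.1.3 draws it by placebo multiple imputation (pMI). If some window days exist, SAP 5.1.1 divides the attack count by the days with information and multiplies by 7, with no minimum number of days. The SAP does not say which rule applies to a partial week, or which day anchors week 4 for a subject who never has a Visit 4.

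Sections 1.3 and 4.5 also describe the QTcF stop differently: one ends treatment, the other ends study participation. A site cannot tell from them whether diary entry may continue.

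**Working it through.** **Day-count convention, checked against the plan.** Protocol 3.1 puts Visit 5 on Day 42-49 for a last dose on Day 28. 28 + 14 = 42 and 28 + 21 = 49, so two to three weeks means +14 to +21 days.

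**Inputs.**
- d = day of last dose.
- E = Early Termination day = d + 14 to d + 21 (Protocol 4.5, 7.1.5).
- V = Visit 4 day, nominally 28, permitted 26 to 29 (Protocol 7.1.4, SAP 5.1.1).
- Week-4 window = Days V - 7 to V - 1.
- The visit day itself is not counted. The protocol states this for the baseline week (4.1); I assume the same for week 4.

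**Formula.** Window days available = max(0, min(V - 1, E - 1) - (V - 8)). For V = 28 this is max(0, min(27, E - 1) - 20).

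**Results for V = 28 (window Days 21-27).**

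| Last dose, d | Early Termination, E | Last full diary day | Window days out of 7 |
|---|---|---|---|
| 1 | 15-22 | 14-21 | 0-1 |
| 2 | 16-23 | 15-22 | 0-2 |
| 6 | 20-27 | 19-26 | 0-6 |
| 7 | 21-28 | 20-27 | 0-7 |
| 13 | 27-34 | 26-33 | 6-7 |
| 14 | 28-35 | 27-34 | 7 |

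Day 7 is the first last-dose day that can give a full week (visit at three weeks). Day 14 is the first that always does (visit at two weeks).

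**Sensitivity to V.** A full week needs E to be at least V.
- Visit at +21: d must be at least V - 21, so the cut-off is Day 5, 6, 7 or 8 for V = 26, 27, 28 or 29.
- Visit at +14: d must be at least V - 14, so the cut-off is Day 12, 13, 14 or 15.
- Counting the visit day as a diary day lowers each cut-off by one.

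**Visit 2 QTcF stop (d = 1).** The latest E is Day 22, so the last full diary day is 21. That leaves at most 3, 2, 1 or 0 window days for V = 26, 27, 28 or 29 (at most 4 if the visit day counts). It is never a full week.

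**What scaling one day means.** With one observed day, SAP 5.1.1 gives attacks / 1 x 7. One attack more or fewer on that day moves the weekly value by 7. The planned treatment difference is 12.0 - 4.0 = 8.0 attacks per week.

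**How many subjects.** Planned dropout is 10% of 80 = 8. The documents give no timing of dropout, so the number stopping early enough to be affected is anywhere from 0 to 8.

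**After the fix.** With the diary open through the end of the window, all 7 days can be recorded whatever d is. A Day 1 stop goes from 0-1 to 7 available days.

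**The case against.** The plan foresees this loss. SAP 5.1.3 names week-4 diaries missing through early discontinuation and imputes them from the placebo arm, a method it describes as conservative. For a subject who took one dose about four weeks earlier, placebo-like behaviour is among the easier assumptions to defend. Preferring observed off-treatment data is partly a choice of estimand.

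Power is not at risk on the plan's own figures. The t-test needs 26 per group (power 80.7%). 26 / 0.9 = 28.9, so 29 per group or 58 in total, against 80 planned. Losing all 8 dropouts leaves 36 per group and a power of about 92%.

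The QTcF route may be rare. Entry requires a mean QTcF of at most 450 msec and the stop is above 480, so a subject at the entry ceiling needs a rise of more than 30 msec, about twice the mean rises of 12.0-16.1 msec reported in Protocol 1.3. That section calls those findings uncertain and reports no drug-related change in GS-1001.

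All of this stands, and it limits the size of the point. It does not answer two things. The missing days could be recorded at almost no cost. And it is unclear whether a partial week goes to pMI or is multiplied up from one day, a case for which the conservative argument is not made.

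**Conclusion.** This is a modest, cheap improvement. At nominal Day 28, a last dose before Day 7 can never give a full week-4 diary, and only a last dose on Day 14 or later always does. The Visit 2 QTcF stop falls short of a full week under every permitted Visit 4 day.

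A reader might infer more than the documents support:
- **That the data cannot exist whatever window is used.** With Visit 4 on Day 26 and a visit at three weeks, a last dose on Day 5 or 6 gives all seven days, and a Day 1 stop gives three.
- **That the primary outcome is lost for every first-week stopper.** A partial week can still yield a value under SAP 5.1.1. A total loss is certain only where no window day is recorded, for example a Day 1 stop seen at two weeks.
- **That the loss falls on the active arm and favours the drug.** An imbalance is possible through QTcF stops but is not shown, and pMI draws active-arm dropouts from placebo.
- **That a particular number of subjects is affected.** Assuming that half of the 8 planned dropouts stop in the first week would give 4, but nothing in the documents supports that share.

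The conclusion rests on two assumptions: the visit day is not a diary day, and Day 28 is the anchor for subjects without Visit 4.

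**What to change.** 1. **Protocol 7.1.5 and Appendix 2.** Keep the eDiary open through Day 28 for any subject who stops IMP early and has not withdrawn consent to data collection. The window ends on Day 27; Day 28 allows the diary's question about the previous day to confirm Day 27. The Early Termination visit stays where it is. Section 4.5 already treats withdrawal of consent separately, so the exception is easy to word.
2. **SAP 5.1.1 and 5.1.3.** Anchor week 4 at nominal Day 28 for subjects without a Visit 4. Use the observed diary where it is available and pMI only where it is missing. State how many days make a week evaluable. For diaries already closed, report the number of window days by arm.
3. **Protocol 1.3 and 4.5.** The two descriptions of the QTcF stop must be reconciled so that stopping IMP and ending data collection are stated as separate events. I take no position on the stopping rule itself.

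**Cost.** A short protocol amendment, an SAP edit and an eDiary setting. A few subjects make home entries for up to about two more weeks (at most 28 - 15 = 13 days after an Early Termination visit on Day 15). Because the eDiary is now collected at Visit 5, a later remote closing or device-return step is also needed. No extra site visit or procedure is added.
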